4.6.2. Benefit Assessment

Since this Phase I study is being conducted in healthy subjects with normal renal function; in subjects with mild, moderate, and severe renal impairment; and in subjects with ESRD (on and not on hemodialysis), there is no direct clinical benefit to study subjects. Participation in this study will contribute to the process of developing new antibiotic therapies in areas of growing unmet need.

4.6.3. Overall Benefit:Risk Conclusion

The risk of adverse events (AEs) is minimized for the populations being investigated in the proposed study by careful selection of dose and subjects for the study; the relatively short duration of study drug exposure; and the extent of safety monitoring incorporated into the study.

5. SELECTION OF STUDY POPULATION AND WITHDRAWAL CRITERIA

Specific information regarding warnings, precautions, contraindications, AEs, and other pertinent information on the GSK investigational product or other study treatment that may impact subject eligibility is provided in the IB.

Deviations from inclusion and exclusion criteria are not allowed because they can potentially jeopardize the scientific integrity of the study, regulatory acceptability, or subject safety. Therefore, adherence to the criteria as specified in the protocol is essential.

5.1. Inclusion Criteria

A subject will be eligible for inclusion in this study only if all of the following criteria apply:

AGE
1. Male or female subject between 18 and 80 years of age, inclusive.

TYPE OF SUBJECT AND DIAGNOSIS INCLUDING DISEASE SEVERITY
2. Healthy subject must be in clinically stable health as determined by the investigator based on medical history, clinical laboratory results (serum chemistry, hematology, urinalysis, and serology), vital sign measurements, 12-lead electrocardiogram (ECG) results, and physical examination findings. Subject with renal impairment must have clinical laboratory values consistent with their disease and are approved by the investigator.
3. Subject with renal impairment (mild, moderate, severe, or subjects with ESRD) may be taking medications, which in the opinion of the investigator, are believed to be therapeutic but do not affect study drug absorption, distribution, metabolism, or excretion. These medications must be stable doses taken for at least 7 days before the first dose of study drug. Any exceptions will be discussed with the sponsor or medical

monitor on a case-by-case basis and the reasons documented.

4. Subject with normal renal function or renal impairment (estimated eGFR corresponding to the calculated eGFR [the estimated eGFR may be rounded to the nearest integer]) at Screening (Section 6.2).
5. Subjects with ESRD on hemodialysis should be on hemodialysis for at least 3 months before Screening and is able to tolerate a hemodialysis treatment lasting 3 to 4 hours with blood flow rates of >200 mL/min.
6. Alanine aminotransferase (ALT) and bilirubin $1.5 \times$ upper limit of normal (ULN; isolated bilirubin >math>1.5 \times</math> ULN is acceptable, if bilirubin is fractionated and direct bilirubin <math><35\%</math>).

WEIGHT

7. Body weight ≥ 50 kg and BMI within the range 18.5 and 40 kg/m², inclusive.

SEX

8. Male or Female

A female subject is eligible to participate if she is not pregnant (as confirmed by a negative serum human chorionic gonadotrophin test), not lactating, and at least one of the following conditions applies:

- a Nonreproductive potential defined as:
 - Premenopausal females with one of the following:
 - Documented tubal ligation
 - Documented hysteroscopic tubal occlusion procedure with follow-up confirmation of bilateral tubal occlusion
 - Hysterectomy
 - Documented bilateral oophorectomy
 - Postmenopausal defined as 12 months of continuous spontaneous amenorrhea (in questionable cases a blood sample will be obtained to test for simultaneous follicle-stimulating hormone and estradiol levels consistent with menopause (refer to laboratory reference ranges for confirmatory levels). Females on hormone replacement therapy (HRT) and whose menopausal status is in doubt will be required to use one of the highly effective contraception methods if they wish to continue their HRT during the study. Otherwise, they must discontinue HRT to allow confirmation of post-menopausal status prior to study enrollment.
- b Reproductive potential and agrees to follow 1 of the options listed below in the GSK Modified List of Highly Effective Methods for Avoiding Pregnancy in Females of Reproductive Potential ([Appendix 7](#)) requirements from 30 days prior to the first dose until completion of the Follow-up Visit.
- c For subjects with indeterminate pregnancy test results or a persistently low human chorionic gonadotropin results, nonpregnancy status must be documented by other means (subjects with ESRD only).

The investigator is responsible for ensuring that subjects understand how to properly use

methods of contraception.

INFORMED CONSENT

- | |
|----------------------------------------------------------------------------------------------------------------------------------------------------------------------------------------------|
| 9. Capable of giving signed informed consent as described in Section 10.2, which includes compliance with the requirements and restrictions listed in the consent form and in this protocol. |
|----------------------------------------------------------------------------------------------------------------------------------------------------------------------------------------------|

5.2. Exclusion Criteria

A subject will not be eligible for inclusion in this study if any of the following criteria apply:

CONCURRENT CONDITIONS/MEDICAL HISTORY (INCLUDES LIVER FUNCTION AND QTc INTERVAL)

- | |
|-----------------------------------------------------------------------------------------------------------------------------------------------------------------------------------------------------------------------------------------------------------------------------------------------------------------------------------------------------------------------------------------------------------------------------------------------------------------------------------------------------------------------------------------------------------------------------------------------------------------------------------------------------------------------------------------------------------------------------------------------------------------------------------------------------------------------------------------------------------------------------------------------------------------------------------------------------------------------------------------------------------------------------------------------------------------------------------------------------------------------------------------------------------------------------------------------------------------------------------------------------------------------------------------------------------------------------------------------------------------------------------------------------------------------------------------------------------------------------------------------------------------------------------------------------------------------------------------------------------------------------------------------------------------------------------------------------------------------------------------------------------------------------------------------------------------------------------------------------------------------------------------------------------------------------------------------------------------------------------------------------------------------------------------------------------------------------------------------------------------------------------------------------------------------------------------------------------------------------------------------------------------------------------------------------------------------------------------------------------------------------------------------------------------------------------------------------------------------------------------------------------------------------------------------------------------------------------|
| 
 1. Subject has a clinically significant abnormality in past medical history or at the Screening physical examination (excluding renal insufficiency and other related stable medical conditions within the renally impaired population of subjects [e.g., hypertension, diabetes, or anemia, which should be stable for at least 3 months before the first dose of study drug]) that in the investigator's opinion may place the subject at risk or interfere with outcome variables of the study. This includes, but is not limited to, history or current cardiac, hepatic, neurologic, gastrointestinal (GI), respiratory, hematologic, or immunologic disease. 2. Subject has any surgical or medical condition (active or chronic) that may interfere with drug absorption, distribution, metabolism, or excretion of the study drug, or any other condition that may place the subject at risk, in the opinion of the investigator. 3. Subject has a functioning renal transplant. 4. Subject with renal impairment has a systolic blood pressure outside the range of 90 to 200 mm Hg, a diastolic blood pressure outside the range of 45 to 110 mm Hg, or a heart rate outside the range of 40 to 120 bpm. 5. Subject with renal impairment has a hemoglobin value <9 g/dL. 6. Female subject has a positive pregnancy test result or is lactating at Screening or upon admission to the clinic. 7. Use of a systemic antibiotic within 30 days of Screening 8. Within 2 months before Screening, either a confirmed history of Clostridium difficile diarrhoea infection or a past positive Clostridium difficile toxin test. 9. Subject has a history of drug and/or alcohol abuse within 6 months before Screening, as determined by the investigator, or subject has a positive drug screen at Screening or upon admission to the clinic. For subjects with renal impairment, a positive drug screen result related to the use of prescription medications is allowed per investigator review and approval, and tetrahydrocannabinol use is allowed per investigator review and approval. 10. History of sensitivity to any of the study drugs, components thereof, or a history of drug or other allergy that, in the opinion of the investigator or GSK medical monitor, contraindicates their participation. 11. History of sensitivity to heparin or heparin-induced thrombocytopenia (if the clinic |
|-----------------------------------------------------------------------------------------------------------------------------------------------------------------------------------------------------------------------------------------------------------------------------------------------------------------------------------------------------------------------------------------------------------------------------------------------------------------------------------------------------------------------------------------------------------------------------------------------------------------------------------------------------------------------------------------------------------------------------------------------------------------------------------------------------------------------------------------------------------------------------------------------------------------------------------------------------------------------------------------------------------------------------------------------------------------------------------------------------------------------------------------------------------------------------------------------------------------------------------------------------------------------------------------------------------------------------------------------------------------------------------------------------------------------------------------------------------------------------------------------------------------------------------------------------------------------------------------------------------------------------------------------------------------------------------------------------------------------------------------------------------------------------------------------------------------------------------------------------------------------------------------------------------------------------------------------------------------------------------------------------------------------------------------------------------------------------------------------------------------------------------------------------------------------------------------------------------------------------------------------------------------------------------------------------------------------------------------------------------------------------------------------------------------------------------------------------------------------------------------------------------------------------------------------------------------------------------|

uses heparin to maintain IV cannula patency).

CONCOMITANT MEDICATIONS

12. Subject has used medications known to affect the elimination of serum creatinine (e.g., trimethoprim or cimetidine) or competitors of renal tubular secretion (e.g., probenecid) within 30 days before dosing.
13. Subjects cannot use any over-the-counter, or prescription medication (except for hormonal contraceptives and/or acetaminophen; see Section 6.11 for more details), vitamin supplement, or herbal medication within 7 days (or 5 half-lives, whichever is longer) before dosing and during the study within 7 days before dosing and during the study. Any exceptions (including subjects with renal impairment that will be on medications during the study) will be discussed with the sponsor or medical monitor on a case-by-case basis and the reasons will be documented.

DIAGNOSTIC ASSESSMENTS AND OTHER CRITERIA

14. Subjects with normal renal function have a presence of hepatitis B surface antigen or positive hepatitis C antibody test result at Screening or within 3 months prior to first dose of study treatment. A subject with renal impairment with stable hepatitis C who has normal liver function test results is allowed with investigator approval.
15. A positive test for human immunodeficiency virus antibody.
16. Subject has clinically significant abnormal findings in serum chemistry, hematology, or urinalysis results obtained at Screening or Day -1 (and Day 7 for Group F only), other than those associated with underlying renal conditions or other stable medical conditions consistent with the disease process.
17. Subject with normal renal function has a baseline corrected QT interval using the Fridericia formula (QTcF) of >450 milliseconds (msec) and subject with renal impairment has a baseline QTcF of >480 msec.

OTHER EXCLUSION CRITERIA

18. Donation of blood in excess of 500 mL within 12 weeks prior to dosing or participation in the study would result in donation of blood or blood products in excess of 500 mL within a 56 day period.
19. Previous exposure to gepotidacin within 12 months prior to the first dosing day.
20. The subject has participated in a clinical trial and has received an investigational product within the following time period prior to the first dosing day in the current study: 30 days, 5 half-lives, or twice the duration of the biological effect of the investigational product (whichever is longer).
21. Subject is unable to comply with all study procedures, in the opinion of the investigator.
22. The subject should not participate in the study, in the opinion of the investigator or Sponsor.

5.3. Screening/Baseline/Run-in Failures

Screen failures are defined as subjects who consent to participate in the clinical trial but are never subsequently dosed. In order to ensure transparent reporting of screen failure subjects, meet the Consolidated Standards of Reporting Trials publishing requirements, and respond to queries from regulatory authorities, a minimal set of screen failure information is required including demography, screen failure details, eligibility criteria, and serious adverse events (SAEs).

5.4. Withdrawal/Stopping Criteria

The following actions must be taken in relation to a subject who fails to attend the clinic for a required study visit:

- The clinic must attempt to contact the subject and reschedule the missed visit as soon as possible.
- The clinic must counsel the subject on the importance of maintaining the assigned visit schedule and ascertain whether or not the subject wishes to and/or should continue in the study.
- In cases where the subject is deemed “lost to follow-up”, the investigator or designee must make every effort to regain contact with the subject (where possible, 3 telephone calls, emails, or text messages; and, if necessary, a certified letter to the subject’s last known mailing address or local equivalent methods). These contact attempts should be documented in the subject’s medical record.
- Should the subject continue to be unreachable, only then will he/she be considered to have withdrawn from the study with a primary reason of “lost to follow-up.”

A subject may withdraw from study treatment at any time at his/her own request, or may be withdrawn at any time at the discretion of the investigator for safety, behavioral, or administrative reasons. If a subject withdraws from the study, he/she may request destruction of any samples taken, and the investigator must document this in the clinic study records.

5.4.1. Liver Chemistry Stopping Criteria

Liver chemistry stopping and increased monitoring criteria have been designed to assure subject safety and evaluate liver event etiology in alignment with the FDA guidance, “Drug-Induced Liver Injury: Premarketing Clinical Evaluation,” [DHHS, 2009].

Study treatment will be stopped if the following liver chemistry stopping criterion is met:

- $ALT \geq 3 \times ULN$

Although stopping criteria for continued dosing of investigational product due to liver chemistry parameters are not applicable for single-dose studies, and, in this case, for subjects that will receive the gepotidacin dose twice (Group F), if subjects are found to have values consistent with usual stopping parameters, it is appropriate to institute evaluation and monitoring criteria according to standard GSK criteria. Therefore, liver

function tests should be evaluated according to stopping criteria and work-up instituted if defined parameters are reached.

For details of the required assessments if a subject meets the above criteria, refer to [Appendix 2, Liver Chemistry Follow-up Procedures](#).

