In Part 2 (optional) of the study, subjects in Group F will participate in 2 treatment periods, with dosing in these periods separated by a washout period of at least 7 days. Subjects in Group F will enter the clinic at Check-in (Day -1, Period 1 and Day 7, Period 2) before each study drug administration (Day 1, Period 1 and Day 8, Period 2). On Day 1 (Period 1) and Day 8 (Period 2), subjects in Group F will receive a single dose of study drug as follows: gepotidacin 750 mg administered as a 2-hour IV infusion starting approximately 2 hours before the initiation of the last hemodialysis session of the week (Period 1) and gepotidacin 750 mg administered as a 2-hour IV infusion starting within 2 hours after completion of the last hemodialysis session of the week (Period 2). Subjects in Group F will be discharged from the clinic on Day 10 of Period 2 after all scheduled PK and safety assessments have been completed, and will return to the clinic for a Follow-up Visit approximately 10 days (± 5 days) after the last dose administration in Period 2. The duration of the study (from Screening to the Follow-up Visit) will be approximately 50 days.

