4.6.1. Risk Assessment

Potential Risk of Clinical Significance	Summary of Data/Rationale for Risk	Mitigation Strategy
Investigational Product (IP) Gepotidacin		
Gastrointestinal (GI) Effects	
Lower GI effects (soft stools, flatulence, and diarrhoea) are the most common GI-associated adverse events (AEs) reported in human subjects dosed with gepotidacin.
 
In the Phase I studies, out of approximately 400 healthy subjects who have received gepotidacin, C. difficile has been reported in 8 subjects.
	
Exclusion criterion and close monitoring of clinical parameters and AEs will be conducted to mitigate and assess GI effects.
 
Patients with significant GI symptoms will obtain the appropriate work-up (Appendix 8).
 
Subject stopping criteria: Subjects experiencing Grade 3 or Grade 4 AEs will have permanent discontinuation of the investigational medication and will be followed as appropriate until resolution of the AE.

Cardiovascular Effects Reversible increase in QT prolongation and a mild increase in heart rate in human subjects.	In Study BTZ115775 [see GlaxoSmithKline Document Number 2015N227098_00 Study ID BTZ115775], the infusion of gepotidacin at a dose of 1000 mg and 1800 mg over 2 hours caused a mild heart rate effect of approximately 6 bpm to 10 bpm and a QT prolongation, measured as $\Delta\Delta\text{QTcF}$, of 12 msec to 22 msec. The QT prolongation evolved during the infusion and was quickly reversed over 2 hours after the end of the infusion. Blood pressure observations were within normal ranges.	
Exclusion criteria, close monitoring of clinical parameters, and AEs will be conducted and stopping criteria will be utilized to mitigate and assess cardiovascular effects.
 
Note: Subjects with a QRS duration <70 and >120 msec will be excluded.
 
Subject stopping criteria: Subjects experiencing a QTcB and/or QTcF >500 msec and/or a change from baseline in QTc >60 msec.

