Rash/Hypersensitivity	
A fine, mild, generalized pruritic macular skin rash was seen in 3 of 8 subjects following 10 days of dosing 1500 mg 3 times daily (see the report of Study BTZ115198).
 
Rash was reported as an AE for 4 of 122 subjects (3%) and consisted of mild, related urticaria; moderate, related rash maculopapular; mild, related rash; mild, related urticaria; and mild, not related arthropod bite (see report of Study ID BTZ116704).
 
There has been no other evidence of hypersensitivity in human subjects to date.
	
Exclusion criterion: History of sensitivity to any of the study drugs, components thereof, or a history of drug or other allergy that, in the opinion of the investigator or GlaxoSmithKline medical monitor, contraindicates their participation.
 
Subject monitoring: Patients will be monitored closely for cutaneous effects throughout the study, and specialist advice will be sought as needed to evaluate any clinically significant finding.
 
Subject stopping criteria: Grade 3 or higher rash or Grade 2 rash with evidence of systemic involvement.

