5.4.3. Gastrointestinal Stopping Criteria

Subjects experiencing Grade 3 or Grade 4 AEs (confluent pseudomembranes or ulcerations OR mucosal bleeding with minor trauma; tissue necrosis OR diffuse spontaneous mucosal bleeding OR life-threatening consequences, e.g., aspiration, choking) will be followed as appropriate until resolution of the AE(s).

Furthermore, subjects who experience diarrhoea or enteritis should be evaluated with additional fecal occult blood tests and stool cultures as deemed appropriate by the investigator as outlined in [Appendix 8](#) and [Appendix 9](#).

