5.4.4. Rash/Hypersensitivity Stopping Criteria

A subject presenting with a Grade 3 AE or higher rash (diffuse macular, maculopapular, OR morbilliform rash with vesicles or limited number of bullae; OR superficial ulcerations of mucous membrane limited to 1 site) or a Grade 2 rash (diffuse macular, maculopapular, or morbilliform rash; OR target lesions) with evidence of systemic involvement will be followed as appropriate until resolution of the AE(s).

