
 Report the event to GSK within 24 hours Complete the Liver Event CRF, and complete an SAE data collection tool if the event also meets the criteria for an SAE^b Perform liver event follow-up assessments Monitor the subject until liver chemistries resolve, stabilize, or return to within baseline (see MONITORING below) 
MONITORING:
 
If ALT $\geq 3 \times$ ULN AND bilirubin $\geq 2 \times$ ULN or INR >1.5
 
 Repeat liver chemistries (include ALT, AST, alkaline phosphatase, bilirubin) and perform liver event follow-up assessments within 24 hours Monitor subjects twice weekly until liver chemistries resolve, stabilize, or return to within baseline A specialist or hepatology consultation is recommended 
If ALT $\geq 3 \times$ ULN AND bilirubin <2 \times ULN and INR ≤ 1.5:
	
 Viral hepatitis serology^c Serum creatine phosphokinase and lactate dehydrogenase. Fractionate bilirubin, if total bilirubin $\geq 2 \times$ ULN Obtain complete blood count with differential to assess eosinophilia Record the appearance or worsening of clinical symptoms of liver injury, or hypersensitivity, on the AE report form Record use of concomitant medications on the concomitant medications report form including acetaminophen, herbal remedies, other over the counter medications. Record alcohol use on the liver event alcohol intake case report form 
If ALT $\geq 3 \times$ ULN AND bilirubin $\geq 2 \times$ ULN or INR >1.5:
 
 Anti-nuclear antibody, anti-smooth muscle antibody, Type 1 anti-liver kidney microsomal antibodies, and quantitative total immunoglobulin G (IgG or gamma

Liver Chemistry Stopping Criteria – Liver Stopping Event	

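### Group F is the only group with a second dose, yet Section 5.4.1 appears to exempt it from the ALT stop, and Sections 5.4.3 and 5.4.4 leave out the stopping action that Section 4.6.1 attaches to GI and rash events

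*Protocol*

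**What the plan says.** **Dosing.** Under protocol Section 4.2, Groups A to E receive one infusion. Group F, in optional Part 2, is dosed on Day 1 and Day 8: "Subjects in Group F will enter the clinic at Check-in (Day -1, Period 1 and Day 7, Period 2) before each study drug administration".

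**Liver.** Section 5.4.1 opens with "Study treatment will be stopped if the following liver chemistry stopping criterion is met" and gives ALT ≥3 × ULN. The next paragraph says that stopping criteria for continued dosing are "not applicable for single-dose studies, and, in this case, for subjects that will receive the gepotidacin dose twice (Group F"), and asks for evaluation, monitoring and work-up. Appendix 3 still classes ALT ≥3 × ULN as a liver stopping event, but its main actions are to report, assess and follow: "Monitor the subject until liver chemistries resolve, stabilize, or return to within baseline".

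**GI.** Section 4.6.1 says "Subjects experiencing Grade 3 or Grade 4 AEs will have permanent discontinuation of the investigational medication", together with follow-up. In Section 5.4.3, headed as GI stopping criteria, the list of Grade 3 and 4 events is followed only by "aspiration, choking) will be followed as appropriate until resolution of the AE(s").

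**Rash.** Section 4.6.1 has "Subject stopping criteria: Grade 3 or higher rash or Grade 2 rash with evidence of systemic involvement". Section 5.4.4 uses the same thresholds and ends "with evidence of systemic involvement will be followed as appropriate until resolution of the AE(s").

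**The concern.** A rule that withholds a later dose can operate only where a later dose exists, and that is Group F alone. The usual reason for setting aside stopping criteria, that a single-dose study has nothing left to stop, does not carry over to a group dosed again a week later. Yet Group F is the group that Section 5.4.1 names.

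At stake is whether a subject with ESRD who met a liver, GI or rash threshold after Period 1 receives a second infusion. Section 4.6.2 states that subjects have no direct clinical benefit, so the rule should not depend on which section a site consults. The study is multi-center, and two sites could handle the same event differently.

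**Working it through.** No power or precision figure is involved. The check is a comparison of texts with a little arithmetic on the schedule.

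**1. Doses at risk.** Group F size is about 4 to 8 (Section 4.3), with one second dose each: 4 × 1 = 4 to 8 × 1 = 8. If Group F is not enrolled, the number is 0.

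**2. Instructions side by side.**

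| Event | Where a stop is stated | What the Section 5.4 subsection says |
|---|---|---|
| ALT ≥3 × ULN | 5.4.1, first statement; Appendix 3 label | 5.4.1 then sets the criteria aside, naming Group F; work-up only |
| QTc thresholds | 5.4.2 | Subject is withdrawn |
| Grade 3 or 4 GI event | 4.6.1, permanent discontinuation | 5.4.3: follow-up only |
| Grade 3 or higher rash, or Grade 2 with systemic involvement | 4.6.1, by its label; no action spelled out | 5.4.4: follow-up only |

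Three of the four subsections (5.4.1, 5.4.3, 5.4.4) lack one clear stopping action. Only 5.4.2 has it.

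**3. Two readings of the Section 5.4.1 sentence.** Either the Group F phrase belongs with the clause that sets the criteria aside, which is the natural reading and exempts the group. Or it belongs with the later clause, so that Group F also gets a work-up and the opening stop still holds. The sentence does not settle which applies.

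**4. Appendix 3, footnote a.** This discontinues treatment when ALT is ≥3 × ULN, bilirubin is ≥2 × ULN and fractionation is not immediately available. It does not cover an isolated ALT rise.

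**5. What the Day 7 recheck catches.** Table 4 repeats the eligibility criteria and laboratory tests on Day 7. Inclusion 6 uses 1.5 × ULN for ALT; the operator is lost in the text, and I take it as an upper limit. Exclusion 16 covers clinically significant Day 7 laboratory findings. Section 5 disallows deviations from the criteria and Section 7 bars waivers, except for immediate safety concerns. An ALT above 1.5 × ULN on Day 7 therefore blocks the second dose. To pass inclusion 6, an ALT that reached 3 × ULN must have fallen by a factor of at least 3 ÷ 1.5 = 2. Measured from the Day 2 sample, it has 7 − 2 = 5 days to do so.

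**6. GI and rash at Day 7.** No criterion names these events. Exclusions 2 and 22 rest on opinion. Exclusion 10 applies if a rash is judged a history of sensitivity to the drug.

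**7. Timing.** The 24-hour laboratory result is due before Day 3 discharge. Appendix 3 asks for repeat liver tests within 24 hours, or within 24 to 72 hours for an isolated ALT rise. The latest due time is Day 3 + 72 h = Day 6, and 8 − 6 = 2 days before the second dose. No turnaround is given for the repeat, but the first result alone comes 8 − 3 = 5 days ahead. The event would be seen in time; the instruction is what is unclear.

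**The case against.** The strongest case on the other side is that little here is a true contradiction. A site can follow Sections 4.6.1 and 5.4.3 together: discontinue, and follow to resolution. Nothing in Section 5.4.3 or 5.4.4 permits redosing. The rash thresholds match, and both places carry a stopping label. For the liver, the second reading in step 3 leaves the stop in force, and Appendix 3 keeps its stopping-event label without excepting Group F. Section 5.4.1 also points to a flow chart in Appendix 2 that is not readable here and might carry the action. Section 5.4 lets the investigator withdraw anyone for safety, and the Day 7 recheck imposes a numerical ALT limit.

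Most of this stands, and it sets the size of the point. GI and rash are omissions, and the GI one is sharper because Section 4.6.1 spells out the action there. The liver gap is narrowed to ALT values that recover by Day 7. What remains is that Section 5.4.1, read naturally, undoes its own stop for the one group where that stop matters. Sections headed as stopping criteria state no stop, and discretion allows a dose to be withheld without requiring it.

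A reader might infer that the protocol directs sites to redose after a severe GI event or rash. It does not: the instruction is incomplete, and Section 4.6.1 still applies.

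**Conclusion.** The point holds as a wording fault with a safety consequence, and it should be corrected before Group F is enrolled. Section 5.4.1 is in tension with itself over Group F. Section 5.4.3 drops a discontinuation that the sponsor requires elsewhere, and Section 5.4.4 names no stopping action.

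About 4 to 8 second doses are at risk if Group F is enrolled. A reader might take that as the number of subjects affected; it is not, because only those with a qualifying Period 1 event are. The documents give no rate for such events, so I state no probability. A reader might also infer that a subject with a raised ALT could simply be redosed; the Day 7 criteria do not support that. The liver exposure is mainly an ALT that reached 3 × ULN after Period 1 and was within the limit by Day 7. For GI and rash, withholding the second dose rests on Section 4.6.1 and on investigator judgement.

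This assumes the natural reading of Section 5.4.1 and an upper limit in inclusion 6. Nothing is inferred from the Appendix 2 chart; if it states a stop for Group F, the liver part becomes a matter of aligning the text with it.

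**What to change.** Use the sponsor's own thresholds.

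- **Section 5.4.1:** remove the words that extend the non-applicability to Group F. State that a Group F subject with ALT ≥3 × ULN after the Period 1 dose does not receive the Period 2 dose, whatever the Day 7 value. Check that the Appendix 2 chart agrees.
- **Section 5.4.3:** add the permanent-discontinuation wording from Section 4.6.1 ahead of the follow-up clause.
- **Section 5.4.4:** state that a subject meeting the existing thresholds has study treatment stopped, including any infusion in progress, and receives no further dose. The infusion clause matters in every group, since all receive a 2-hour infusion.
- **Section 6.3**, which allows the Period 2 dose to be reduced, should cross-refer to Section 5.4.

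No new threshold, visit or review body is needed. The cost is that an affected subject gives Period 1 data only, which in a group of about 4 to 8 is a noticeable loss for Period 2. Section 4.3 already allows replacement after premature discontinuation.
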